Description: Wisepill is a real-time, wireless, electronic adherence monitoring device used to assess ART adherence in real time.^{54,55} Wisepill uses cell phone technology to transmit a real-time signal to a web server when the pill box is opened. Participants do not need to come into the clinic for the study to obtain readings. A dose will be considered 'taken' if the box is opened \pm 2 hours from the prescribed time.⁵⁴ The study will also use the recommended methods for Wisepill data collection and analysis, which are to adjust for technical malfunctions, loss of signal, and self-reported pocket doses.^{54,55} Participants in both conditions will be given a Wisepill box at the baseline visit, and the 2-week period between baseline and randomization will serve as the baseline adherence measure. We will calculate % doses missed vs. prescribed. Participants will use the Wisepill box during the first three months of the study (which maps onto the intervention period), and return the device at their post-treatment assessment.

Time Frame: Approximately 10-weeks post-randomization (post-intervention assessment)

B. Substance Use

a. **Title:** Biological measure of substance use (alcohol, drugs)

Description: Biological measure of substance use. Drug use will be assessed using urinalysis (rapid detect 6-panel urine tests (cocaine, marijuana, amphetamines, opiates, phencyclidine, alcohol).

Time Frame: Approximately 10-weeks post-randomization (post-treatment assessment, primary outcome) and 22-weeks post-randomization (6-month follow-up assessment, secondary outcome)

b. **Title:** WHO-ASSIST

Description: Score on the Alcohol, Smoking, and Substance Involvement Screening Test (WHO-ASSIST). The WHO-ASSIST was developed for the World Health Organization (WHO), and is used to detect and manage substance use and related problems in primary and general medical care settings. The test screens for alcohol, cannabis, cocaine, opiates, amphetamines, hallucinogens, and other drug-related problems in primary care and has been validated in South Africa. It categorizes individuals into low (0-3 for illicit drug use), moderate (4-26 for illicit drug use), or high risk (>26 for illicit drug use) for substance use related problems.

Time Frame: Approximately 10-weeks post-randomization (post-treatment assessment: primary outcome) and 22-weeks post-randomization (6-month follow-up assessment: secondary outcome)

C. Feasibility & Acceptability of Intervention

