4. Chart Extraction: Patients who provide informed consent will also be invited to sign a release of information to allow access to their medical record for current ART regimen, time on ART, viral load, CD4 count, tuberculosis (TB) treatment information, mental health information (including diagnoses and substance use treatment referrals) and appointment attendance (HIV treatment program and Matrix if applicable). This information will be specifically extracted from their medical charts at all major assessments.

E. Data analytic plan.

Power calculation and sample size.

The study plans to enroll 60 participants. The main analysis which the sample size calculation was based on is the effect of the intervention vs. enhanced standard of care on ART nonadherence (Wisepill) at 6 months. Previous objective measures of ART adherence in substance using populations have estimated average adherence of approximately 55% with a standard deviation of 0.25.⁷⁴⁻⁷⁶ Assuming similar characteristics in standard of care, and based on a sample size of 30 in each arm as recommended as the upper limit sample size for pilot RCTs, the study will have 80% power to detect an 18% difference in objectively measured ART adherence between study arms using a two-sided test with an alpha level of 0.05. Given that the intervention will be adapted and has not been implemented prior in this setting, the table has been included below to demonstrate the levels of power based on varying differences in average adherence that may be detected between groups. These estimates are based on 30

participants in each arm, in keeping with the recommendations for pilot RCTs and pilot,⁷⁷ Type I hybrid-effectiveness-implementation designs.^{23,53}

Data analytic plan.

Quantitative longitudinal analysis will examine changes in primary effectiveness outcomes: 1) ART nonadherence; 2) substance use; 3) and viral load (exploratory) from baseline to 6-month follow-up between the conditions. Descriptive measures will be used to summarize data (e.g., means, SD, median, IQR for continuous variables). Exact binomial confidence intervals will be used to estimate confidence intervals for categorical variables.

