Statistical tests (such as t-test and Wilcoxon rank sum test) will be used to compare continuous study outcomes (e.g., ART nonadherence) between the two arms at baseline. For comparison of categorical outcomes (e.g., urinalysis), Fisher's exact test will be used. Longitudinal data analysis using generalized linear mixed models (GLMM) will be used to compare the study endpoints (ART nonadherence, substance use, viral load at 6 months) between the two arms after adjusting for the effect of other covariates (e.g., gender, age). This approach increases power by including all available data points. Intent-to-treat will be utilized, where all individuals will be analyzed according to the condition that they were randomized. Effect size estimates will be generated to provide estimates to power for a larger future grant application.

Table 1. Levels of power based on varying differences in adherence detected.

Predicted Avg Adherence in Control Group	Predicted Avg Adherence in Tx Group	Difference in Avg Adherence	SD of Estimated Adherence	Power
0.55	0.85	0.30	0.25	0.99
0.55	0.80	0.25	0.25	0.97
0.55	0.75	0.20	0.25	0.88
0.55	0.73	0.18	0.25	0.80
0.55	0.70	0.15	0.25	0.64
0.55	0.65	0.10	0.25	0.34

ETHICAL CONSIDERATIONS AND RISKS TO THE SUBJECTS

A. Risks to participants.

Human subjects involvement and characteristics.

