Quantitative. Quantitative longitudinal analysis will examine changes in ART nonadherence, substance use, and viral load from baseline to post-treatment between the conditions. If appropriate after examining descriptive data, normality, and assumptions, T-tests may be used to compare continuous variables (e.g., age, ART nonadherence) and Fisher's exact test may be used to compare categorical variables (e.g., gender, urinalysis). If the appropriate statistical assumptions are met after examining distributions of main outcome variables, longitudinal data analysis using generalized linear mixed models (GLMM) will be used to compare the two study arms over time. This approach increases power by including all available data points. We will adjust the analyses for relevant baseline demographic characteristics (e.g., gender, age) for each analysis, and clinical differences that exist between the two treatment arms. Intent-to-treat analyses will be utilized, where all individuals will be analyzed according to the condition to which they were randomized.

The published version of our protocol paper that outlines this data analytic plan can be found online at:

Magidson, J. F., [name], J. A., [name], B., Belus, J. M., Regenauer, K. S., [name], L. S., ... & [name], S. A. (2020). Project Khanya: A randomized, hybrid effectiveness-implementation trial of a peer-delivered behavioral intervention for ART adherence and substance use in Cape Town, South Africa. *Implementation Science Communications*, 1, 23. doi: [10.1186/s43058-020-00004-w](https://doi.org/10.1186/s43058-020-00004-w)

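### The protocol's outcome section makes week 10 primary for urinalysis and WHO-ASSIST, its analysis section runs to 6 months, the SAP runs to post-treatment, and no document names the contrast that tests the primary substance-use outcome

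*Protocol*

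**What the plan says.** Protocol section D.1.B gives the time frame for urinalysis as "Approximately 10-weeks post-randomization (post-treatment assessment, primary outcome) and 22-weeks post-randomization (6-month follow-up assessment, secondary outcome". WHO-ASSIST has the same two times with the same ranking.

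Protocol section E, under the data analytic plan, lists the primary effectiveness outcomes and the window over which change is examined: "2) substance use; 3) and viral load (exploratory) from baseline to 6-month follow-up between the conditions". A later sentence says that generalized linear mixed models (GLMM) will "compare the study endpoints (ART nonadherence, substance use, viral load at 6 months) between the two arms", with covariate adjustment and use of every available data point.

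The SAP (Effectiveness Outcomes, Quantitative) sets a shorter window: "changes in ART nonadherence, substance use, and viral load from baseline to post-treatment between the conditions". If model assumptions are met, "longitudinal data analysis using generalized linear mixed models (GLMM) will be used to compare the two study arms over time". It does not mention the 6-month visit.

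**The concern.** The outcome section ranks the two visits, but neither analysis text carries the ranking over. An analyst working from section E could report the 6-month difference as the substance-use result. One working from the SAP would most likely report week 10 and might not report week 22. A third could report an overall arm-by-time test. Each could claim to follow the plan.

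The choice matters because the two visits compare different amounts of treatment. After session 6, intervention participants may attend up to six booster sessions before the 6-month visit. Control participants are referred to a 16-week Matrix program. If begun at randomization, it would still be running at week 10 and could be finished by week 22. The arm difference may therefore change between visits, and a choice made after both results are known could change the conclusion.

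**Working it through.** **1. Visits on one clock.** Randomization is about 2 weeks after baseline (protocol section C). Week 10 is then 10 + 2 = 12 weeks from baseline, the 3-month post-treatment visit. Week 22 is 22 + 2 = 24 weeks from baseline, the 6-month visit. The week-22 outcomes in D.1.B and the 6-month follow-up in section E are the same visit.

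**2. The texts side by side, for substance use.**

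| Place | Time | Rank of the time points | Contrast named |
|---|---|---|---|
| Protocol D.1.B | week 10 and week 22 | primary and secondary | none (outcome definition) |
| Protocol E, change sentence | baseline to 6-month visit | none; outcomes called primary | none |
| Protocol E, GLMM sentence | 6 months, or no time if the phrase belongs to viral load | none | arm comparison, at 6 months at most |
| SAP | baseline to post-treatment | none | arms compared over time |

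The change sentence in section E is the firmer evidence, because its window plainly covers substance use.

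**3. What post-treatment means in the SAP.** D.1.B and the table of measures at major assessments use the term for the week-10 visit and list the 6-month visit separately. The assessment-visit text in section C and the human-subjects text also describe both follow-ups as post-treatment assessments. On the natural reading the SAP stops at week 10, which agrees with the primary time point in D.1.B but leaves week 22 unnamed. On the broad reading it covers both visits without ranking them.

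**4. Tests the model allows.** Urinalysis is also done mid-way in both arms: at session 3 in the intervention arm and at about week 5 in the control arm. A longitudinal model then yields at least three tests: the arm difference at week 10, the arm difference at week 22, and an overall arm-by-time test. Using all data points does not choose among them.

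**5. The plan's own figure.** The only power figure is for Wisepill adherence: 30 per arm, difference 0.18, SD 0.25, two-sided 0.05. The standardized difference is 0.18 / (0.25 × √(2/30)) = 0.18 / 0.0645 = 2.79, and power is Φ(2.79 − 1.96) = 0.796, against 0.80 stated. It reproduces, but it has no bearing on substance use, for which no power is given.

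**6. Cost of an open time point.** Suppose one measure is tested at both visits at two-sided 0.05 and either result may be called the endpoint. With independent tests, the chance of at least one false positive is 1 − (1 − 0.05)² = 0.0975. For correlated tests, one million pairs of standard normal statistics with correlation r were simulated, counting pairs with |z| > 1.96 for either:

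| r (assumed) | False-positive rate |
|---|---|
| 0 | 0.097 |
| 0.3 | 0.096 |
| 0.5 | 0.090 |
| 0.7 | 0.083 |
| 0.9 | 0.071 |

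The documents give no correlation between visits, so the range is shown. The figures are per measure.

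**The case against.** The best defence is that D.1.B is explicit for both measures, so the primary time point is declared. A longitudinal window to 6 months includes week 10 and need not displace it, and the SAP, read naturally, agrees with D.1.B. The phrase about 6 months in the GLMM sentence may qualify viral load alone. The trial has 60 participants, is sized by pilot recommendations, and is meant to supply effect sizes for a larger study. All of this stands. It narrows the conflict mainly to D.1.B against section E, and it limits the seriousness. It does not supply the missing contrast.

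A reader might also infer more than the documents support:

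- *That the 22-week outcomes have no analysis.* Section E runs to the 6-month visit with a GLMM. The SAP is titled supplemental and does not say that it replaces section E. The gap is that the SAP does not name these outcomes and that no separate week-22 contrast is defined.
- *That the trial would lose its only evidence on lasting change in substance use.* AUDIT, Timeline Followback and the SIP are also scheduled at the 6-month visit.
- *That the error rate is 8% to 10%.* That holds only if the time point is treated as open, and D.1.B gives good reason not to do so.

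**Conclusion.** The point holds in a limited form and should be fixed. For urinalysis and WHO-ASSIST, the ranking in D.1.B is not carried into either analysis text, section E points to a later visit than the declared primary one, and the SAP does not name the declared secondary visit. The primary substance-use test is therefore not fixed. If that freedom were used, the false-positive rate per measure would rise from 5% to about 8% to 10%, for assumed correlations of 0.7 to 0 and two-sided tests at 0.05; at 0.9 it would be about 7%. No sample-size or power figure changes.

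**What to change.** For substance use only, state the following in protocol section E and in the SAP:

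- Fit one longitudinal model per measure, using the pre-randomization value and all scheduled post-randomization measurements, including the mid-point urinalysis. For WHO-ASSIST, the table of measures places the pre-randomization value at screening.
- The arm difference at week 10 is the primary contrast and the arm difference at week 22 is the secondary contrast. Both are always reported.
- The reference to 6 months in the GLMM sentence of section E is not the primary substance-use time point.

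Do not simply replace post-treatment with both weeks throughout the SAP sentence. That sentence also covers ART nonadherence, and the Wisepill device is returned at the post-treatment visit, so the edit would prescribe a week-22 analysis of data that will not exist. Leave the Wisepill wording there at post-treatment.

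The cost is wording in two documents. The visits and measurements are already scheduled, and the ranking is the one the sponsor set in D.1.B. The change should be made before outcomes are examined by arm.

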clinic as failing first line treatment in the past 3 months: VL > 400 copies/mL, on second-line treatment, reinitiated on first-line treatment within the past three months, or pharmacy non-refill at least once in the past three months) will be screened for substance use. Eligible patients will be briefed on study procedures, and if interested, will provide informed consent. All individuals meeting inclusion criteria will be provided the opportunity to participate.

Based upon preliminary studies and published work screening for substance use in HIV care^{7,26,27} the study estimates to recruit 1-2 eligible patients per week. At this rate, the study can conservatively estimate recruiting and randomizing 60 patients feasibly within 1.5 years.

Retention. Bilingual research assistants will track retention. Staff will be trained to place reminder calls to participants 1 week and then three days prior to each scheduled follow-up session. This approach has been used successfully in past work by the US team, and has achieved an 84% retention rate at 3-month follow-up. Each participant will also be asked for updated contact information (e.g. phone number, address) at each follow-up assessment to ascertain if phone numbers have changed.

C. Study Procedures

Study setting. This study will be conducted through the University of Cape Town (UCT). The proposed clinic (where Phase 1 data collection also occurred) and where the parent study (010/2014) is being conducted is the Town II clinic in Khayelitsha.

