Study recruitment and retention	Research Meeting Report - RA to study team	Monitored frequently by PI at research team meetings
Enrollment and Randomization	Research meeting report of enrollment updates (inclusion and exclusion criteria) and tracking of assignment to condition	Monitored frequently by PI at research team meetings
Self-report data	RA will review data at participants' visits for completeness, accurate downloading of data, and tracking	Monitored frequently by PI at research team meetings
Intervention	A random selection of 20% of sessions for each therapist will be reviewed for therapist adherence to protocol by PI	Monitored at frequent clinical supervision

Confidentiality.

Confidentiality is assured as participants will be identified on all study materials only by participant number, visit number, and date of visit. By recording the study data in this manner, the information can be considered 'de-identified.'

F. Data safety and monitoring plan.

Regulatory Issues

The following procedures will be followed, in compliance with NIH requirements, to ensure the safety of study participants and the validity and integrity of data.

Mechanisms for reporting adverse events.

Adverse events are defined as harmful occurrences to study participants, either study related or non-study related.

At yearly intervals during the course of the study and then again at its completion, unblinded summaries of the numbers and rates of adverse events by treatment group will be summarized by the research team. These reports will include types of events, severity, and treatment phase. Data on individual non-serious adverse events is not expected to be needed.

Reporting of SAEs to the IRB and NIDA.

Expedited review will occur for all events meeting the FDA definition of Serious Adverse Events (SAEs; i.e., any fatal event, immediately life-threatening event, permanently or substantially disabling event, event requiring or prolonging inpatient hospitalization, or any

congenital anomaly). This also includes any event that a study investigator or the DSM Committee judges to impose a significant hazard, contraindication, side effect, or precaution. Additional reporting to site-specific IRBs will be done within 24 hours of the study team being made aware of the SAE. Reporting of any study-related SAEs and SAEs that severely impact participants (i.e., participant deaths) will be made to NIDA within 24-72 hours of the study team being made aware of the SAE.

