Reporting of IRB actions to NIDA.

The principal investigator will report, via email, and, if appropriate hard copies of action logs or reports, of any major IRB actions. These will also be reported on the written, yearly progress report to NIDA. Minor amendments (i.e. advertisements, minor changes to procedures) are not regularly reported to NIDA.

Report of changes or amendments to the protocol.

Any changes to the protocol or amendments will be submitted to the IRB before they are implemented. For each yearly annual review, the detailed protocol will be updated and sent to the IRB as well.

Following guidelines by NIH, the NIDA project officer will be kept informed of any major changes to the protocol prior to being conducted via email from the principal investigator to the project officer. This will include any changes involving key personnel. Additionally, these changes will be recorded in the annual progress report submitted to the NIDA project officer.

Trial stopping rules.

There are no articulated stopping rules in advance of this study (i.e. for futility or for a stronger than expected effect). However, if at any time during the course of the study the Committee judges that risk to subjects outweighs the potential benefits, the Committee shall have the discretion and responsibility to recommend that the study be terminated. In such cases, the PI will immediately consult the DSM committee and consider the most appropriate course of action up to and including the immediate discontinuation of the intervention. There is no pre-specified stopping rule given the low anticipated risk of participation and small sample size. The power analysis is such that the full N would be required to make this determination. However, as with any DSMB, this DSMB will have the power to request analyses, post-randomization data, or any other information about the study, and has the power to suspend the study should they deem it necessary and a potential participant safety issue.

Disclosure of any conflict of interest.

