For the purposes of this study, all SAEs will be required to be reported to the Committee, regardless of any judgment of their relatedness to the study. All relevant information will be reported to the DSMB for each SAE including information about the event and its outcome, study condition, concomitant medications, the subject’s medical history and current conditions, and all relevant laboratory data. This will be provided annually at the DSMB committee meeting.

Reporting to site-specific IRBs will be done within 24 hours of the study team being made aware of the SAE. Reporting of any study-related SAEs and SAEs that severely impact participants (i.e., participant deaths) will be made to NIDA within 24-72 hours of the study team being made aware of the SAE.

Non-Serious Adverse Events. At yearly intervals during the course of the study and then again at its completion, the DSMB will be provided with unblinded summaries of the numbers and rates of adverse events by treatment group. These reports will include types of events, severity, and treatment phase. Data on individual non-serious adverse events is not expected to be needed for this review.

Other Safety-Related Reports. At yearly intervals throughout the course of the study, the DSMB will also receive unblinded summary reports of treatment retention and reasons for dropout, by treatment arm and study phase.

Trial Efficacy

Plans for interim analysis for efficacy data.

If at any time during the course of the study, the Committee judges that risk to subjects outweighs the potential benefits or a safety concern arises, the Committee shall have the discretion and responsibility to recommend that the study be terminated. However, there are no pre-specified interim analysis for efficacy data given that (1) this is not an efficacy trial, rather a hybrid effectiveness-implementation trial; (2) the low anticipated risk of participation in the behavioral intervention and (3) small sample size. The power analysis is such that the full N would be required to make this determination. However, the DSMB will have the power to request analyses should they deem it necessary.

DSM Plan Administration

Responsibility for data safety and monitoring.

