The principal investigator and primary mentor are ultimately responsible for data and safety monitoring. The processes described above ensure that the principal investigator will be aware of important study related issues on a regular basis. If any staff becomes aware that an adverse event occurs, this will immediately report it to the principal investigator and site project director. In addition, a yearly DSM committee review of all SAEs will occur.

To fulfil its mission of ensuring the safety and integrity of the study, it is necessary that the DSM Committee be comprised of members who possess a high degree of competence and experience, as well as the ability to function independently of all other parties involved in the

study. The DSMB members will function free of the career and financial interests of its members and will consist of three members with experience in conducting clinical intervention research for psychiatric and substance use disorders, expertise in biostatistics, and a thorough knowledge of clinical trial ethics and human subject protection issues.

Frequency.

The DSM Committee will be updated annually with a report containing randomization data as well as adverse events. These adverse events are tracked for IRB submission as well. All SAEs are reported annually at continuing review. The DSM Committee will be comprised of nominees from both the Cape Town and US study sites.

Content of DSM report

The DSM report will include a tally and description of adverse events and serious adverse events. It will include a description of how these were handled, which experimental group the participant was assigned to (treatment or control), and if and how the participants' physician was notified. The DSM meeting will also involve a presentation from the P.I. regarding any emerging clinical issues involved in delivering the treatment, expected versus actual recruitment rates, treatment retention rates, any quality assurance or regulatory issues that occurred during the past year relevant to the trial, and any actions or changes with respect to the protocol. Sections of the DSM report will include:

- A. Brief description of the trial
- B. Baseline sociodemographic characteristics
- C. Retention and disposition of study participants
- D. Q.A. Issues
- E. Regulatory Issues
- F. AEs
- G. SAEs
- H. Efficacy

DSM Board Plan

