Members. The Data and Safety Monitoring Board (DSMB) will function as an independent body charged with ensuring that the safety of study subjects is protected in Phase 3 and that the scientific goals of the study are being met. To support those purposes, the DSMB will review any proposed major amendments to the study protocol at the annual review, perform ongoing monitoring of drop-outs and all adverse events, determine whether study procedures should be changed or the study should be halted for reasons related to the safety of study subjects, and perform periodic review of the completeness and validity of data to be used for analysis of safety and efficacy. The DSMB will also ensure subject privacy and research data confidentiality. The DSM Committee will include both US- and South Africa-based investigators.

The Chairperson of the DSMB will communicate by e-mail and telephone conference with the other members. Reporting and communication about other matters will occur on a yearly basis, for the duration of Phase 3. Decisions of the DSMB will be made based on a majority vote of the members.

Conflict of interest. The DSMB members will function free of the career and financial interests of its members.

Protection of confidentiality. Adverse event reports and annual summaries will not include identifiable information. Each report will only include the participants' identification numbers.

Monitoring activities. At a minimum, the DSMB report includes an overview of the progress of participant intake and retention; summary reports describing participant compliance with visits, evaluations, and dosing as described in the protocol; a summary of all adverse events and major amendments to the protocol; and a summary of the completeness and quality

of key data elements needed to characterize participants, their dosing, and their primary and secondary outcomes. These reports are used by the DSM Committee to evaluate the capacity of the data capture and processing to support scientifically valid analyses. For ease of understanding, reports are done graphically, similarly to the CONSORT figures.

Communication plan to IRB and NIDA. The annual IRB Continuing Review will include the DSMB report for review. DSMB activity will be reported in annual NIH progress reports when applicable.

LIST OF MEASURES

A description of each measure can be found above in the outcomes section.

Table 1. Measures at Major Assessments

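### Individual SAE information reaches the DSMB only once a year, which conflicts with its role of acting at any time and monitoring all adverse events continuously

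*Protocol*

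**What the plan says.** All of this is in section F of the protocol (Data safety and monitoring plan). The SAP does not deal with safety monitoring.

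**What the DSMB is asked to do.** Under Trial stopping rules, the Committee is to recommend termination "if at any time during the course of the study the Committee judges that risk to subjects outweighs the potential benefits". The section on interim analysis repeats this. Under DSM Board Plan, Members, the board is to "perform ongoing monitoring of drop-outs and all adverse events". No numerical stopping rule is set.

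**What the DSMB is given, and when.** Collection and reporting of AEs to SAEs requires every SAE to be reported to the Committee, whether or not it is judged related. The information for each event includes study condition, history, concomitant medication and laboratory data. The only timing attached is: "This will be provided annually at the DSMB committee meeting". Responsibility for data safety and monitoring adds: "In addition, a yearly DSM committee review of all SAEs will occur". The Frequency paragraph likewise describes an annual update, and the by-group summaries of adverse events are also yearly.

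**What others are given.** Staff report adverse events to the PI immediately. For the IRBs: "Additional reporting to site-specific IRBs will be done within 24 hours of the study team being made aware of the SAE". NIDA hears within 24-72 hours, but only of study-related SAEs and those that severely affect participants.

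**Expedited review.** Reporting of SAEs to the IRB and NIDA, and later Collection and reporting of AEs to SAEs, both promise it for SAEs. Neither says who performs it or how quickly.

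**The concern.** The board's duty and its supply of information run on different clocks. A body that is to weigh risk against benefit at any time, and to follow all adverse events as they arise, needs to learn of a serious event soon after it occurs. As written, it may learn of it up to a year later.

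This matters because the DSMB is the body the plan describes as independent, and the one to which it gives unblinded summaries by arm. The IRBs and the PI see single events quickly, but the plan does not assign them the by-arm comparison. The paragraph on expedited review also covers events that the Committee itself judges to be a significant hazard, and it cannot make that judgement about an event it has not been told of.

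The interval is long relative to the trial. A participant's whole course is about 6 months from baseline, with the six sessions delivered over about 8 weeks, so a yearly cycle can span a participant's entire time in the study.

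**Working it through.** **Step 1: the texts side by side.**

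| Section of the protocol | Timing for the DSMB |
|---|---|
| Trial stopping rules; interim analysis | may recommend termination at any time |
| DSM Board Plan, Members | ongoing monitoring of all adverse events |
| Collection and reporting of AEs to SAEs | per-SAE information yearly |
| Responsibility; Frequency | SAE review and update yearly |
| Reporting of SAEs to the IRB and NIDA | expedited review, with no reviewer or timeline named |

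The first two rows call for prompt information, the next two give a yearly supply, and the last does not settle the matter.

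**Step 2: inputs for the size of the gap.**

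- Sample size N = 60 (Power calculation and sample size: "The study plans to enroll 60 participants").
- Planned accrual of 1 to 2 per week (Recruitment procedures: "the study estimates to recruit 1-2 eligible patients per week").
- Conservative accrual, from the same section: "the study can conservatively estimate recruiting and randomizing 60 patients feasibly within 1.5 years".
- Assumptions not in the documents: accrual is steady, and the date of the first DSMB review is measured from first enrolment.

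**Step 3: reproduce the plan's own accrual figure.** Weeks to full enrolment = 60 / rate.

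- At 1 per week: 60 / 1 = 60 weeks.
- At 2 per week: 60 / 2 = 30 weeks.
- Both are inside 1.5 years (78 weeks), so the stated period is consistent with the stated rate. The conservative period implies 60 / 78 = 0.77 per week.

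**Step 4: number enrolled by the first review.** Enrolled = min(60, rate × weeks).

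| First review | 60 over 78 weeks | 1 per week | 2 per week |
|---|---|---|---|
| 6 months (26 weeks) | 60 × 26/78 = 20 | 26 | 52 |
| 9 months (39 weeks) | 60 × 39/78 = 30 | 39 | 78, capped at 60 |
| 12 months (52 weeks) | 60 × 52/78 = 40 | 52 | 104, capped at 60 |

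**Step 5: randomized rather than enrolled.** Randomization follows baseline by about two weeks, so 50 weeks of accrual count at month 12.

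- 60 × 50/78 = 38.5 at the conservative rate.
- 50 at 1 per week.
- 100, capped at 60, at 2 per week.

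With 30 planned per arm, half of each gives about 19, 25 and 30 assigned to the intervention.

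**Step 6: those who have already finished.** Participants enrolled in the first 26 weeks would have reached their 6-month assessment by month 12. From the first row of the table in step 4, that is 20, 26 or 52.

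**The case against.** The case on the other side has four parts.

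1. **There may be a faster route.** The paragraph promising expedited review names the DSM Committee and calls IRB reporting additional. DSM Board Plan has the chair using e-mail and telephone, puts communication about other matters on a yearly footing, and mentions adverse event reports separately from annual summaries. These hints suggest that prompt contact may have been intended. None gives a route or timeline to the DSMB, so they make the text more ambiguous without removing the conflict.

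2. **DSMB judgement is not the only safeguard.** A reader might infer from the absence of a stopping rule that nothing else protects participants. The documents do not support that. The PI and primary mentor hold ultimate responsibility, the PI hears of events at once and can consider discontinuing the intervention, the IRBs hear within 24 hours, and individual referral procedures exist. A reader might also infer that the DSMB can act only after most participants are enrolled. That is too strong, because the board may request any information and may suspend the study. What remains is narrower: nothing stated tells it when there is something to request.

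3. **The date of the first meeting is unknown.** This stands. An annual cycle does not fix its starting point, so any count of participants is conditional.

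4. **Light monitoring is proportionate.** The trial tests six counselling sessions in 60 people, and the protocol cites low anticipated risk and small size. That is a fair reason for having no numerical stopping rule or interim analysis. It does not explain why a report already due to the IRBs within a day should not also go to the board, and the protocol does plan for emergency care and for dangerous withdrawal symptoms.

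**Conclusion.** The point holds as an internal conflict in the safety plan. The DSMB's SAE information is set to a yearly cycle, its duties are continuous, and the expedited-review wording does not bridge the two. The gap is confined to notifying the independent board that sees data by arm and does not extend to all safety oversight.

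On size, if the first review is 12 months after first enrolment and accrual is steady at the plan's own rates, 40, 52 or 60 of 60 would be enrolled. A reader might take 40 to 60 as a certainty, but the documents do not date the meeting, and at 6 months the range is 20 to 52. Enrolment also overstates exposure: at 12 months about 19 to 30 people would have been assigned to the intervention. The documents give no expected SAE rate, so the number of events that would go unseen cannot be estimated. The conflict in the text does not depend on any of these counts.

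**What to change.** In Collection and reporting of AEs to SAEs, replace the yearly supply of individual SAE information with a requirement that each SAE report goes to the DSMB chair at the same time as the 24-hour IRB report. Keep the annual meeting for the cumulative summary by arm.

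Then align the other sections:

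- **Reporting of SAEs to the IRB and NIDA**, and the expedited-review sentence in **Collection and reporting of AEs to SAEs**: say who carries out expedited review and when.
- **Responsibility for data safety and monitoring**, and **Frequency**: make clear that the yearly review is cumulative and is not the board's first sight of an SAE.
- **DSM Board Plan**: list SAE notification as an exception to the yearly communication. The chair's e-mail and telephone contact with members, and the rule that reports carry identification numbers only, already fit this.

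The cost is a protocol wording change and one more recipient for a report already being written, with minor extra administration. Design, sample size and analysis are unaffected.
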